13 STATISTICAL CONSIDERATIONS

13.1 Statistical hypothesis

The primary outcome variable is the peak score of the National Institutes of Health-Chronic Prostatitis Symptom Index (NIH-CPSI) total score measured from baseline to six weeks post brachytherapy. The primary hypothesis is that the mean of the primary outcome variable will be ½ standard deviation lower in patients taking Q-Urol compared to placebo.

Version Date: 11APR2023

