1 OBJECTIVES

1.1 Primary Objective

1.1.1 To assess the difference in prostatitis symptoms in men with localized prostate cancer following brachytherapy taking Q-Urol relative to placebo.

Primary Endpoint: The mean peak score of the National Institutes of Health-Chronic Prostatitis Symptom Index (NIH-CPSI) measured at six weeks post brachytherapy.

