4 STUDY DESIGN

4.1 Description

This is a Phase 2, double-blinded, placebo-controlled trial assessing the safety of Q-Urol use after brachytherapy placement in patients with localized prostate cancer. Patients will be randomized in a 1:1 ratio to receive Q-Urol/Placebo twice daily for six weeks after brachytherapy placement. Questionnaires will be administered pre- and post-treatment to assess the change in prostatitis symptoms and quality of life measures. The mean values between groups will be compared.

Once 42 patients (21 to each arm) have been enrolled and treated on the study therapy, enrollment will be placed on hold and an interim analysis conducted. The interim analysis will be conducted for futility and efficacy and will be reviewed by the DSMC. If the analysis is favorable, as defined in the Statistical Analysis section, the trial will open to the enrollment of 98 additional subjects, 49 per arm. However, if the analysis does not demonstrate standards defined in the statistical analysis, the trial will be closed to accrual.

Version Date: 11APR2023

Safety monitoring will be overseen by the DSMC at HCI. See Section 12.4 for safety monitoring plan and early stopping rules.

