12.3.2 Evaluable for response

A modified intent-to-treat data set will be used to assess efficacy. Subjects who have successfully undergone brachytherapy and received one dose of Q-Urol will be evaluable for response. Subjects who fail to undergo brachytherapy or begin Q-Urol therapy will be replaced. Those who do not complete the end of treatment patient questionnaires will be considered treatment failures.

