13.2 Statistical Analyses

13.2.1 Sample size determination

The outcome for sample size determination is the primary endpoint variable, the peak of the National Institutes of Health-Chronic Prostatitis Symptom Index (NIH-CPSI) total score measured from baseline to six weeks post brachytherapy. The primary hypothesis is that the mean of the primary outcome variable will be $\frac{1}{2}$ standard deviation lower in patients taking Q-Urol compared to placebo. A single interim analysis is planned after N1= 21 subjects per group have outcome data. The interim and final analysis will compare the treatment and control means using nominal t statistics (control minus treatment). If the t statistic has a value less than -1.16 at the interim analysis the trial will be terminated for futility. If the t statistic has a value greater than 2.85 at the interim analysis the trial will be terminated for efficacy.

If the study is not terminated for efficacy or futility at the interim analysis an additional N2 = 49 patients per group will be accrued for a total of N = 70 patients per group. If the interim analysis is done at the planned sample size (21 patients per group) the treatment will be deemed efficacious at the final analysis if the t statistic has a nominal value greater than 1.67.

The above design was evaluated using 100,000 simulated data sets for both the null and alternative hypotheses. There is 90% power at overall one-sided Type I error equal to 0.05 (one-sided) to detect a 0.5 standard deviation lower mean of the primary endpoint in the treatment group compared to the control group. The probability of early termination for futility under the null hypothesis is 12%. The probability of early termination for futility under the alternative hypothesis is 0.3%. The probability of early termination for efficacy under the alternative hypothesis is 12%.

If the interim analysis or final analysis is performed at a sample size that is different than the planned sample size the final analysis will be adjusted to maintain an overall Type I error of no more than 0.05 (one-sided).

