13.2.2 Primary endpoint

There are two planned analyses of the primary endpoint variable: an interim analysis at N1 = 21 patients per group and a final analysis at N = 70 patients per group. Two sample *t*- statistics will be calculated and evaluated as described in 13.2.1.

Multiple imputation will be used to replace missing end of treatment values of the National Institutes of Health-Chronic Prostatitis Symptom Index (NIH-CPSI) total score. A sensitivity analysis will replace missing values by the largest (i.e. worst) observed value.

In addition to formal testing for a difference between groups, the mean change between groups and the mean change within each group together will be reported together with 95% confidence intervals.

Version Date: 11APR2023

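### The primary NIH-CPSI variable is a peak from baseline to six weeks in Sections 12.2, 13.1 and 13.2.1 but a six-week value in Section 1.1, and the schedule cannot observe a peak

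*Combined protocol and SAP*

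**What the plan says.** Four sections define the primary outcome of the combined protocol and SAP.

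- Section 1.1: "The mean peak score of the National Institutes of Health-Chronic Prostatitis Symptom Index (NIH-CPSI) measured at six weeks post brachytherapy".
- Sections 12.2 and 13.1, in the same words: "peak score of the National Institutes of Health-Chronic Prostatitis Symptom Index (NIH-CPSI) total score measured from baseline to six weeks post brachytherapy".
- Section 13.2.1, as the basis of the sample size: "the peak of the National Institutes of Health-Chronic Prostatitis Symptom Index (NIH-CPSI) total score measured from baseline to six weeks post brachytherapy".

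Table 1 (with note 10) and Section 11.5 schedule the NIH-CPSI twice: at screening and at EOT (Day 43, window +7 days). Section 10.1 allows screening up to 90 days before brachytherapy. The weekly calls cover adverse events, concomitant medication, questions and compliance, not the questionnaire. The form in Appendix 1 asks about the past week.

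Other passages bear on the meaning. Section 2.1 expects symptoms to be worst around weeks 4-6. Section 12.3.2 states: "Those who do not complete the end of treatment patient questionnaires will be considered treatment failures". Section 13.2.2 states: "Multiple imputation will be used to replace missing end of treatment values", and adds that "the mean change between groups and the mean change within each group together will be reported", as a supplement to the formal test. Section 4.1 states: "Questionnaires will be administered pre- and post-treatment to assess the change in prostatitis symptoms and quality of life measures", and then: "The mean values between groups will be compared".

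**The concern.** All four definitions use the word peak. They differ in time frame: one is a value at six weeks, the other three an extreme over an interval that starts at baseline. With only two forms per man, the only interval extreme that can be computed is the larger of the screening and EOT scores. A man whose screening score is the higher then contributes a number recorded before implant and before any capsule, which treatment cannot change.

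This variable is compared with -1.16 and 2.85 at the interim analysis and 1.67 at the final. An analyst following Section 1.1 and one following Section 13 literally would compute different t statistics from the same patients. If the choice is still open when data are available, it can be made with the results in view, and the interim analysis can stop the trial.

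**Working it through.** **1. Can a peak be observed?** The EOT form covers about one week, so at Day 43 it reaches back to about Day 36 (43 - 7). No form covers the weeks between implant and then. The only post-implant value is the EOT score.

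**2. Which readings does the text leave open?**

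| Reading | For | Against |
|---|---|---|
| EOT score | 1.1 (at six weeks); 2.1 (worst at weeks 4-6); 12.3.2 (failure tied to the EOT forms); 13.2.2 (EOT values imputed) | from-baseline wording in 12.2, 13.1, 13.2.1 |
| max(screening, EOT) | literal wording of 12.2, 13.1, 13.2.1 | 1.1; no passage spells it out |

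**3. The plan's own figures.** Inputs from Section 13.2.1: 21 then 70 per group, effect 0.5 SD, boundaries -1.16 / 2.85 / 1.67. By hand, using the final analysis only, the mean of t is 0.5 × √(70/2) = 0.5 × 5.916 = 2.958, and power is about Φ(2.958 - 1.67) = Φ(1.288) = 0.901. Simulation of the full two-stage design (200,000 trials per hypothesis, normal data):

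| Quantity | Stated | Simulated |
|---|---|---|
| Power | 90% | 90.1% |
| Type I error, one-sided | 0.05 | 0.050 |
| Futility stop, null | 12% | 12.6% |
| Futility stop, alternative | 0.3% | 0.3% |
| Efficacy stop, alternative | 12% | 12.6% |

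The design reproduces. The calculation is in SD units, so it belongs to whichever variable carries the 0.5 SD effect.

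**4. How the maximum dilutes an effect on the EOT score.** The documents give no NIH-CPSI mean, SD or correlation, so everything from here is assumed. Take screening mean 8, SD 5; placebo EOT mean 15, SD 7; correlation 0.3; true effect 3.5 points (0.5 SD) on the EOT score, so the treated EOT mean is 11.5. Write M for the maximum, b for the screening mean, e for the EOT mean, and α = (e - b)/θ. Ignoring the 0-43 limits:

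- SD of EOT minus screening: θ = √(25 + 49 - 2 × 0.3 × 5 × 7) = √53 = 7.28.
- E[M] = e·Φ(α) + b·Φ(-α) + θ·φ(α).
- E[M²] = (e² + 49)·Φ(α) + (b² + 25)·Φ(-α) + (e + b)·θ·φ(α).
- Placebo: α = 7/7.28 = 0.96; mean 15.65; E[M²] = 284.97; SD = √(284.97 - 15.652²) = 6.32.
- Treated: α = 3.5/7.28 = 0.48; mean 12.98; E[M²] = 202.61; SD = √(202.61 - 12.984²) = 5.83.
- Effect on M: 15.65 - 12.98 = 2.67 points. Pooled SD √((6.32² + 5.83²)/2) = 6.08. Standardised effect 2.67/6.08 = 0.44.
- Approximate power: Φ(0.44 × 5.916 - 1.67) ≈ Φ(0.93) = 0.82, against 0.90 for the EOT score.

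**5. Range over assumptions.** Scores limited to 0-43; screening mean 6, 8 or 10, SD 5 or 6; placebo EOT mean 12, 15 or 18, SD 7; correlation 0.3 or 0.5; effect 3.5 points on the EOT score. That is 3 × 2 × 3 × 2 = 36 combinations, with both readings tested on the same simulated patients.

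| Placebo rise, screening to EOT | Combinations | Power, EOT | Power, maximum |
|---|---|---|---|
| 7 points or more | 20 | about 90% | 80-89% |
| 4-6 points | 12 | 89-90% | 68-80% |
| 2 points | 4 | about 90% | 55-62% |

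The last row is an extreme case that fits poorly with the symptom course in Section 2.1 and the exclusion of baseline AUA scores above 15. At rises of 7 points or more, the standardised effect on the maximum is 0.42-0.49, and the two readings reach different conclusions in about 2-12% of trials. Each reading alone keeps type I error near 5%; accepting whichever is significant gives about 5.3-6.2%.

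**The case against.** The strongest reply is that the documents largely settle the matter. A peak score at six weeks reads naturally as the score at the time symptoms are expected to be worst. The failure rule and the imputation both concern EOT values, and the maximum of screening and EOT is a construction no passage spells out. Moreover, Sections 13.1 and 13.2.1 place the 0.5 SD effect on the primary variable itself, so any single variable meant has 90% power by construction, and the lower figures depend on assumed scores. Much of this stands: the EOT score is the better-supported reading, and no power loss is demonstrated. But three of the four definitions, including the one that sets the boundaries, say something else.

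Stronger readings are tempting. A reader might infer that change from screening is a third candidate, since Section 4.1 speaks of change and Section 13.2.2 reports it. The documents do not support that: Section 13.2.2 reports change in addition to the test, Section 13.2.1 compares treatment and control means, and Section 13.2.3 says change explicitly where change is tested. Nor does the ANCOVA in Section 13.2.4 govern the primary analysis; it is exploratory, and Section 13.2.2 specifies two-sample t statistics. Larger error inflation from choosing among three readings therefore does not apply.

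**Conclusion.** The concern holds as a contradiction in the time frame of the sole primary outcome, combined with a schedule that cannot observe a post-implant peak. Two readings are open, and the EOT score is better supported. The sample size is not in error. The case for correction rests on the contradiction rather than on the power figures: the latter assume score distributions the documents do not give and an effect located on the EOT score. On those assumptions the literal reading costs from about 1 to 10 percentage points of power at placebo rises of 7 points or more, and roughly 10 to 22 at rises of 4-6. The type I error risk from leaving the choice open is small, but removing it costs almost nothing.

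**What to change.** Before the interim analysis, the sponsor should confirm that the six-week score is what is meant. Then:

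- In Sections 1.1, 12.2, 13.1 and 13.2.1 write: *The primary outcome is the NIH-CPSI total score at the EOT (Day 43) visit.* Delete the words peak and from baseline.
- In Section 13.2.2 add: *Change is EOT minus screening; it is reported with 95% confidence intervals and is not tested against the boundaries.*

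The t-test, the 70 per group and the boundaries -1.16, 2.85 and 1.67 stay unchanged. No visit, form or patient is added. The price is giving up any claim to a true peak over the interval, which the current schedule cannot measure. If the sponsor did intend a true peak, rewording will not be enough: NIH-CPSI assessments between Day 1 and Day 43 would be needed.

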13.2 Statistical Analyses

13.2.1 Sample size determination

The outcome for sample size determination is the primary endpoint variable, the peak of the National Institutes of Health-Chronic Prostatitis Symptom Index (NIH-CPSI) total score measured from baseline to six weeks post brachytherapy. The primary hypothesis is that the mean of the primary outcome variable will be $\frac{1}{2}$ standard deviation lower in patients taking Q-Urol compared to placebo. A single interim analysis is planned after N1= 21 subjects per group have outcome data. The interim and final analysis will compare the treatment and control means using nominal t statistics (control minus treatment). If the t statistic has a value less than -1.16 at the interim analysis the trial will be terminated for futility. If the t statistic has a value greater than 2.85 at the interim analysis the trial will be terminated for efficacy.

If the study is not terminated for efficacy or futility at the interim analysis an additional N2 = 49 patients per group will be accrued for a total of N = 70 patients per group. If the interim analysis is done at the planned sample size (21 patients per group) the treatment will be deemed efficacious at the final analysis if the t statistic has a nominal value greater than 1.67.

The above design was evaluated using 100,000 simulated data sets for both the null and alternative hypotheses. There is 90% power at overall one-sided Type I error equal to 0.05 (one-sided) to detect a 0.5 standard deviation lower mean of the primary endpoint in the treatment group compared to the control group. The probability of early termination for futility under the null hypothesis is 12%. The probability of early termination for futility under the alternative hypothesis is 0.3%. The probability of early termination for efficacy under the alternative hypothesis is 12%.

If the interim analysis or final analysis is performed at a sample size that is different than the planned sample size the final analysis will be adjusted to maintain an overall Type I error of no more than 0.05 (one-sided).

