10 STUDY PROCEDURES

10.1 Screening

For screening procedures see the Schedule of Events and the Assessments Section. Screening activities may only begin after a subject has signed consent. All screening activities must take place within 90 days prior to brachytherapy unless otherwise noted.

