11.5 Questionnaire administration

All questionnaires will be completed in the clinic by the patient prior to starting study therapy and after completing six weeks of daily Q-Urol/Placebo therapy.

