13.2.4 Exploratory Analyses

For the analyses involving score changes, the investigators will use ANCOVA in place of 2-sample t-tests, which has been found to be robust to violation of modeling assumptions.

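### Both primary decision tests leave out the pre-treatment NIH-CPSI score, which is already collected; adjusting for it is unused efficiency at almost no cost, not the correction of an error

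*Combined protocol and SAP*

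**What the plan says.** Section 13.2.1 defines the decision statistic: "The interim and final analysis will compare the treatment and control means using nominal t statistics (control minus treatment". The trial stops at 21 per arm if t is above 2.85 (efficacy) or below -1.16 (futility). Otherwise it continues to 70 per arm and succeeds if t exceeds 1.67. Section 13.2.2 confirms that two-sample t "statistics will be calculated and evaluated as described in 13.2.1".

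The pre-treatment score is available. Section 11.5 says "All questionnaires will be completed in the clinic by the patient prior to starting study therapy and after completing six weeks" of therapy, and Table 1 with footnote 10 lists the NIH-CPSI at screening and at end of treatment. Section 10.1 sets the timing: "All screening activities must take place within 90 days prior to brachytherapy unless otherwise noted".

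Outside the decision test, section 13.2.2 says "the mean change between groups and the mean change within each group together will be reported together with 95% confidence intervals", and "Multiple imputation will be used to replace missing end of treatment values" of the score, without stating the imputation model. ANCOVA appears in section 13.2.4, under exploratory analyses: "For the analyses involving score changes, the investigators will use ANCOVA in place of 2-sample t-tests".

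**The concern.** In a randomised trial, a baseline measurement of the outcome can take residual variance out of the treatment comparison. The plan collects that measurement and already regards ANCOVA as sound (13.2.4), yet neither decision uses it. What is at stake is precision. For the same 140 patients, the chance of detecting a real half-SD effect could be somewhat higher and the confidence interval for the primary contrast somewhat narrower. Nothing in the planned test biases the comparison or inflates error.

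**Working it through.** **Inputs from section 13.2.1.** 21 then 70 per arm; effect 0.5 SD; overall one-sided alpha 0.05; bounds 2.85, -1.16 and 1.67. **Assumed.** The baseline-outcome correlation r is not in the documents, so a range is shown.

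**1. The plan's own figures.** The interim noncentrality is 0.5 × √(21/2) = 1.62 on 40 df. This gives a futility stop of 12.6% under the null (plan: 12%), 0.3% under the alternative (plan: 0.3%) and an efficacy stop of 12.4% under the alternative (plan: 12%). Simulating both looks gives power 90.1% and Type I error 0.050. The design reproduces.

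**2. What adjustment does.** Residual variance is multiplied by (1 - r²), so the noncentrality is divided by √(1 - r²). At the final look it is 0.5 × √(70/2) = 2.96 unadjusted, 2.96/0.954 = 3.10 at r = 0.3 and 2.96/0.866 = 3.42 at r = 0.5. The cost is one degree of freedom (40 to 39, 138 to 137) and a small chance-imbalance term. Adjustment breaks even at about r = √(1/(n - 3)) for n patients in total: √(1/137) = 0.09 at the final look and √(1/39) = 0.16 at the interim.

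**3. Two-look power, bounds unchanged, six-week score as outcome.**

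| r | Unadjusted | Adjusted |
|---|---|---|
| 0 | 90.1% | about 90.0% |
| 0.2 | 90.1% | 90.9% |
| 0.3 | 90.1% | 92.2% |
| 0.5 | 90.1% | 95.7% |

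Adjusted Type I error is about 0.05 throughout. Separate runs at r = 0 gave 89.8% to 90.0%; with both tests applied to the same simulated trials the loss is about 0.2 points. The interim is then slightly noisier (efficacy stop 12.1% against 12.4%), which the overall power already includes.

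**4. Interval for the same contrast, 70 per arm, in SD of the six-week score.** The raw-score half-width is 1.977 × √(2/70) = 0.334. Multiplying by √(1 - r²) gives 0.319 at r = 0.3 and 0.289 at r = 0.5. Simulation, which includes the small cost of estimating the slope, gives 0.335 at r = 0, 0.319 at 0.3 and 0.290 at 0.5.

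**5. Does it survive the other reading of the endpoint?** Section 1.1.1 places the score at six weeks, while 12.2 and 13.1 describe a peak from baseline to six weeks. Suppose the outcome is the larger of the two scores, the treated six-week mean is 1 SD above baseline, and the effect is about 0.5 SD on that peak. Unadjusted/adjusted power is then about 90/91% at r = 0 and 90/94% at r = 0.3. At r = 0.5 it is about 91/98% with an effect of 0.51 SD, and about 90/97% with exactly 0.50 SD.

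**6. Missing scores and a bounded scale.** Missing final scores were imputed from arm and baseline and pooled by Rubin's rules. With 10% missing, unadjusted/adjusted power is 87.0/86.8% at r = 0 and 87.1/89.2% at 0.3. With 20% missing it is 82.7/82.6% and 83.6/85.7%. On an integer 0-43 score with a skewed, floor-limited baseline it is 89.8/89.6% at r = 0 and 89.9/92.0% at r = 0.31. Adjusted Type I error stays between 0.049 and 0.052. The missing rates and score distribution are assumptions.

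**The case against.** The strongest objection is that no defect has been shown: a valid test that meets its stated power was chosen over another valid test. That stands, and it is why this is only a suggestion. The correlation may also be low. Section 5.2 excludes AUA scores above 15, section 2.1 attributes the symptoms to the implant, and screening may be up to 90 days earlier. The 95.7% figure needs a correlation that nothing in the documents supports.

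Four stronger readings are tempting, and the documents do not support them.

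- **A large gain in the reported interval.** If the mean change in 13.2.2 is a change-from-baseline contrast, its half-width at r = 0 with equal SDs is 0.472, against 0.335 adjusted. That gain comes from not using change scores. The planned t-test's own interval is 0.334, so adjustment adds nothing there.
- **Baseline enters the primary analysis only through the mean change.** The imputation model in 13.2.2 is unspecified and may include baseline. Section 13.2.4 may also already give an adjusted estimate of that change, though only as exploratory.
- **The planned test falls to about 85% power under the peak reading.** That follows only if 0.5 SD is applied to the six-week score, which is about 0.455 SD on the peak. Section 13.1 sets 0.5 SD on the primary outcome itself, and on that scale the unadjusted power is 90%.
- **The trial is underpowered or its error rate is wrong.** Step 1 shows that neither is so.

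**Conclusion.** The point holds as unused efficiency. Both decisions rest on a valid unadjusted test, and the pre-treatment score that could sharpen it is not in the decision model. If the correlation is 0.3 or less, the realistic gain is 0 to about 2 points of power, and the half-width falls from 0.334 to 0.319 SD at best. At 0.5 the gain is about 5.6 points (95.7 - 90.1). The most that can be lost is about 0.2 points. Type I error and the bounds are unaffected. These sizes rest on the assumed correlations and on simulated score distributions; the direction and the small downside do not depend on the reading of 'peak'. Priority is low, and confidence in the size of the benefit is medium.

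**What to change.** First reconcile the endpoint wording in 1.1.1 with 12.2 and 13.1. The pre-treatment score is a legitimate covariate under either reading. Then, before anyone sees unblinded interim data, amend 13.2.1 and 13.2.2 along these lines:

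- The interim and final statistic is the treatment t (control minus treatment) from a linear model of the primary NIH-CPSI outcome on arm and pre-treatment NIH-CPSI total score. Bounds 2.85, -1.16 and 1.67 are unchanged.
- The multiple-imputation model includes arm and pre-treatment score.
- The adjusted difference is reported with its 95% CI.
- The unadjusted two-sample t-test is kept as a sensitivity analysis.

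Within-arm mean change can still be reported descriptively.

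**Cost.** No new data, visits or patients. One degree of freedom, and at most about 0.2 points of power if baseline is uncorrelated with outcome. It does need a protocol amendment with IRB approval and, under 16.7, FDA review if it is judged to affect scientific quality significantly. The documents do not say whether the interim has taken place. If unblinded results have been seen, the decision test should stay as planned and the adjusted model should be supportive only.
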